8.2.1. Unmasking During the Study Period

Should it be necessary to unmask a subject's treatment assignment in case of emergency, the Investigator may obtain the treatment code for a given randomized subject from the 2-part tear-off label from the subject's IP kit. The randomization code is to be obtained only if a medical emergency exists and knowledge of the medication being taken will influence the medical management of the subject. In the event of emergency or life-threatening condition, the Investigator may need to unmask the subject. The following procedure should be followed:

1. The Investigator should contact the Medical Monitor via phone immediately before unmasking a subject, unless it is not possible to do so without risk to the subject.
2. The Investigator should document the SAE and justification for unmasking in the Study Summary and Comments pages of the eCRF.
3. The subject may continue to participate in the study at the Investigator's discretion. If the subject is to be discontinued from study participation, then ALL procedures described in the Early Discontinuation Visit ([Section 10.4](#)) should be completed.

4. The Investigator should contact Oculos Development Services, LLC (Oculos), the contract research organization, at [contact] within 24 hours with the randomization number, subject initials, details of the AE or SAE, any action taken, and whether the subject is continuing in the study.

8.3. Concomitant Medications

8.3.1. Permitted Medications and Treatments

Therapy considered necessary for the subject's welfare that will not interfere with the evaluation of the IP may be given at the discretion of the Investigator. If there is any question as to whether the medication may interfere, the Investigator should contact the Medical Monitor or Sponsor. Whenever possible, medications should be administered in dosages that remain constant throughout the study duration. Permitted concomitant orally administered medications (including vitamins) should not be taken within 2 hours of study medication dosing.

Artificial tear use is permitted during the study period, but it should be continued at the same frequency and with no change in drop brand.

8.3.2. Prohibited Medications

The Medical Monitor should be notified before prohibited medication or therapy is administered, unless the safety of the subject requires immediate action. The decision to administer a prohibited medication or therapy should be done with the safety of the subject as the primary consideration. The Medical Monitor MUST be contacted to determine the permissibility of a specific medication or therapy and whether or not the subject should continue with study participation.

The initiation or dose modification of systemic medications known to affect tear production is prohibited within 30 days prior to Screening and throughout the study period, but short-term, as-needed dosing of a systemic medication is allowed with certain restrictions. One short (\leq 72 hour) course of a systemic medication that affects tear production (including immunomodulators, tricyclic antidepressants, diuretics, and corticosteroids) or systemic antihistamines is allowed but not within 30 days of Screening or on the day before or the day of any other study visit. Any chronic use of systemic antihistamines within 30 days prior to Screening and throughout the study period is prohibited.

Prescription and OTC ophthalmic mast cell stabilizers and antihistamines are prohibited within 21 days prior to Screening and throughout the study period (systemic mast cell stabilizers are allowed, and systemic antihistamines are permitted with the restrictions outlined above).

Chronic daily use (defined as $>$ 7 consecutive days at the recommended dosing frequency) of oral NSAIDs during the study period is prohibited. ANY use of oral NSAIDs during the study period must be discussed with the Medical Monitor. Aspirin of any dosage is permitted.

Prohibited ophthalmic medications and therapies within 21 days prior to Screening and throughout the study period include the use of any topical prescription ophthalmic medications as follows:

- Cyclosporine (ie, Restasis and Cequa)
- Lifitegrast (Xiidra)
- Steroids
- NSAIDs
- Antiglaucoma medications
- Anti-microbials
- Macrolides

Additionally, oral nutraceuticals (fish, flax, black currant seed oils, etc.), oral tetracyclines, and oral macrolides are prohibited within 21 days prior to Screening and throughout the study period. Isotretinoin (Accutane[®]) is also prohibited within 90 days prior to Screening and throughout the study period.

Contact lens and ophthalmic drop use (eg, artificial tears), while permitted during the study period, are prohibited within designated time periods prior to any study visit. Contact lens wear is prohibited within 12 hours prior to any study visit (subjects determined to have worn contact lenses within 12 hours must be rescheduled), and ophthalmic drop use is prohibited within 2 hours prior to any study visit.

The following procedures are prohibited as specified:

- LASIK or PRK performed within one year prior to Screening and throughout the study period
- History of cauterization of the punctum or existing silicone punctal plug(s); history of silicone plug removal or collagen plug insertion or removal within 12 months prior to Screening and throughout the study period.

8.4. Treatment Compliance

Treatment compliance will be monitored by IP accountability and subjects' daily IP diaries. The amount of unused softgels returned at the Day 42 and Day 84 Visits (IP accountability) and the information provided in the IP diaries by subjects will be documented by study site personnel in the electronic data capture (eDC) system.

8.5. Discontinuation of Investigational Product

Subjects may be discontinued from IP for either of the following reasons:

- The subject has a clinically significant or serious AE that would not be consistent with continuation in the study, as determined by the Investigator or Medical Monitor

- It is possible for subjects to experience a skin rash or other allergic reaction related to the components of the softgels; if this occurs, the subject should discontinue the medication
- Pregnancy

If a subject is discontinued from IP or is generally noncompliant with the protocol, every effort should be made to encourage the subject to continue to attend study visits to be followed for safety, rather than withdrawing the subject from the study. Reasons for considering subject withdrawal from the study are discussed in [Section 7.3](#).

8.6. Investigational Product Materials and Management

8.6.1. Packaging and Labeling

IP will be packaged and labeled at a central packaging facility. Each subject kit will consist of a single box with 5 bottles of IP. Upon randomization, each eligible subject will receive 2 bottles of IP. The study site will retain 3 bottles, 2 of which will be dispensed at the Day 42 Visit, and 1 extra bottle will be maintained at the site in case of loss or damage.

8.6.2. Storage

Store at 15° to 25°C (59° to 77°F). Do not freeze. Keep out of reach of children.

8.6.3. Administration

Following randomization, site personnel will dispense IP and instruct the subject on administration procedures. The daily dose is 4 softgels to be taken at bedtime. No other orally taken medications (including vitamins) should be taken within 2 hours of taking the study medication. If necessary to minimize any digestive upset, subjects may take 2 softgels BID, provided that dosing of study medication is not within 2 hours of a meal or orally taken administration of other medications, including vitamins. Under these circumstances, the first dose should be taken between meals and the second dose should be taken at bedtime.

8.6.4. Dispensing

At randomization, a kit with 2 bottles of IP (sufficient IP to last until the Day 42 Visit with a little overage) and a IP diary will be dispensed to the subject with instructions to return the kit along with all unused IP and the completed study diary at the Day 42 Visit. At the Day 42 Visit, the unused IP will be counted, and the site will dispense 2 bottles of IP (sufficient IP to last until the Day 84 Visit with a little overage) and the IP diary with instructions to return the kit along with all unused IP and the completed study diary at the Day 84 Visit.

8.6.4.1. Interim COVID-19 Pandemic Dispensing Procedures

During the COVID-19 pandemic, sites may dispense to subjects as much IP as necessary (including the fifth/reserve bottle) to allow the subjects to continue to take their study medication until they are able to return for a final visit. In addition, subjects will be dispensed an extra diary with blank study dosing days to be completed if they take IP for more days than originally intended in order to allow continued dosing through to the Final Study Visit.

For those subjects entering the study prior to the pandemic who have not received the remainder of the IP, they can receive the IP and an extra diary with blank study dosing days in any of the following ways:

- In-person during an already scheduled study visit
- In-person pick-up by the subject, or designee, if the subject is unwilling or unable to keep a previously scheduled study visit
- IP and extra diary delivered to the subject by study staff
- IP and extra diary shipped overnight to the subject by study staff

Regardless of the method utilized, study drug accountability records will be maintained, and delivery methods will be documented by the site.

8.6.5. Investigational Product Accountability

The Investigator or designee (eg, study coordinator or pharmacist) will maintain a full accountability record for the IP and will be responsible for recording the receipt, dispensing, and returning all supplies of the IP using the inventories supplied by Oculos. Clinical site personnel will document all dispensed and returned IPs at Baseline (Day 1), Day 42, and Day 84, and IP accountability will be conducted by the monitor at each applicable monitoring visit.

As described in [Section 8.6.4](#), the subject will return all unused IP and the IP diary at Days 42 and 84. The monitor will review dispensing and drug accountability records during site visits and at the completion of the study and will note any discrepancies.

All IP must be stored in a secure facility, with access limited to the Investigator and authorized staff.

9. STUDY ASSESSMENTS

Prior to entry into the study or initiation of any study-related procedures, the subject must read, sign, and date the current IRB-approved version of the informed consent form (ICF). A full discussion of informed consent is presented in [Section 13.3](#).

9.1. Demographic and Background Characteristics

9.1.1. Demographic Information

Demographic information, including date of birth, gender, race, ethnicity, and date of informed consent, will be recorded.

9.1.2. Medical/Ocular History

Clinically significant medical and ophthalmic history will be documented and will include any previously diagnosed ophthalmic abnormalities and ocular surgeries, including laser and non-laser procedures.

9.1.3. Concomitant Medications History

All concomitant medications (prescription and OTC) taken at Screening and for 3 months prior to Screening and throughout the course of the study will be recorded in the Concomitant Medications page of the eCRF. Information regarding the dates of first and last dose, site of dosing (eg, right eye, left eye, both eyes, systemic), and the reason the concomitant medication is being taken must be recorded in the eCRF. When a concomitant medication has been taken at a stable dose for longer than 6 months, an estimation of the start date is adequate. Standard procedural medications will not go into the eCRF but are recorded on a standard procedural medication log provided by Oculos.

9.1.4. Urine Pregnancy Test

A urine pregnancy test will be performed at Screening, at Baseline, and at the Final Study Visit (Day 84) or the Early Discontinuation Visit for women of childbearing potential only.

9.2. Efficacy Assessments

9.2.1. Signs

9.2.1.1. Tear Osmolarity

Tear osmolarity will be tested via the TearLab Osmolarity Test. The osmolarity testing must precede all other diagnostic examinations (except the OSDI at Visit 4), and the subject must refrain from administering any tear supplements within 2 hours prior to the tear osmolarity test. The testing must follow the protocol specified in the Study Procedures Manual. If an invalid reading is obtained (< 275 or > 400 mOsm/L), the investigator should wait at least 10 minutes to retest tear osmolarity. No other diagnostic examinations can be administered until a valid tear osmolarity reading is obtained. Investigators can use up to 3 attempts to obtain a valid reading (with a 10-minute waiting period between attempts).

9.2.1.2. Meibomian Gland Dysfunction Grading

Using a slit lamp at a magnification of 10X to 16X, the eyelids of each eye will be evaluated utilizing the following scales:

Meibomian Gland Dysfunction Grading Scales

A. Meibomian Orifice Size Scale

GRADE	EYELID MARGIN MEIBOMIAN ORIFICE SIZE FINDINGS
0	Orifice barely visible
1	Orifice easily visible in at least 5 orifices
2	Orifice dilated with meibum plug which may extend above the lid margin in at least 5 orifices
3	Orifice keratinized over in at least 5 orifices

A grade of 1 or 2 in meibomian orifice size in at least one eye is required for eligibility into the study. A grade of 0 or 3 in both eyes excludes the subject from study participation. The qualifying osmolarity level and meibomian orifice size grade must be present in the same eye at both Screening and Baseline if only one eye qualifies.

B. Telangiectasia Scale

GRADE	EYELID MARGIN TELANGIECTASIA FINDINGS
0	No blood vessels present between meibomian glands
1	One (1) blood vessel present between 4 pairs of glands/orifices
2	More than 1 vessel between 4 pairs of glands/orifices
3	More than 1 vessel with vasodilation between 4 pairs of glands/orifices
4	More than 1 vessel with vasodilation between 4 pairs of glands/orifices with erythema of the tissue

A certain score on the telangiectasia scale is not required for study entry, nor is it an exclusion criterion. The telangiectasia and meibomian orifice size scales will provide additional detailed information with which to track the progress/resolution of meibomian gland disease.

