11.6.3. Exploratory Efficacy Endpoint

- Proportion of subjects with meibomian gland dysfunction grade of 0 on both meibomian orifice size and telangiectasia scales in the study eye at Visit 4 (Day 84)

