4.2 Endpoints

The two primary efficacy endpoints include mean change from baseline in tear osmolarity in the study eye at Visit 4 (Day 84) and mean change from Screening in Ocular Surface Disease Index (OSDI) score at Visit 4 (Day 84). Secondary efficacy endpoints include mean change from baseline in tear break-up time (TBUT) in the study eye at Visit 4 (Day 84) and mean change from Screening in Schirmer's test (anesthetized) score in the study eye at Visit 4 (Day 84). The proportion of subjects with meibomian gland dysfunction grade of 0 on both meibomian orifice size and telangiectasia scales in the study eye at Visit 4 (Day 84) is an exploratory endpoint.

Safety of OmegaD softgels will be assessed by examination of proportions of subjects experiencing an adverse event during the trial.

5 Study Methods

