Tear osmolarity and OSDI are the primary efficacy assessments. Secondary efficacy endpoints include TBUT and Schirmer's Test. The study eye will be the worse eye at Baseline as defined by higher tear osmolarity score; if both eyes score equally on tear osmolarity, the eye with the lower TBUT score will be chosen, and if still equal, the right eye will be the study eye.

Tear osmolarity will be measured at Screening, Baseline and at Day 84. Tear osmolarity will be assessed using the TearLab Osmolarity Test. Subjects will require tear osmolarity values ≥ 312 mOsm/L in the study eye at both Screening and Baseline. Subjects must have tear osmolarity ≥ 312 mOsm/L and meibomian gland dysfunction grade as defined by a grade 1 or 2 on the meibomian orifice size scale in

at least one eye at both Screening and Baseline. The qualifying osmolarity level and meibomian orifice size grade must be present in the same eye at both Screening and Baseline if only one eye qualifies.

OSDI will be measured at Screening, Day 42 and Day 84. OSDI is assessed on a scale of 0 to 100, with higher scores representing greater disability. The OSDI is a valid and reliable instrument for measuring dry eye disease severity (normal, mild to moderate, and severe) and effect on vision-related function. At screening subjects must have OSDI scores ≥ 20 . This represents at least moderate dry eye disease. OSDI at screening was the pretherapy assessment and will be used as the Baseline value. OSDI was an eligibility criterium and so the screening visit was taken as the baseline value to prevent any issues regarding learning that can occur from repeat testing in a short space of time. It was recognized that OSDI could fluctuate day-to-day. As potential fluctuations were prior to randomization any change would not introduce bias.

TBUT is determined by measuring the interval between instillation of topical fluorescein and appearance of the first dry spots on the cornea. Three consecutive measurements are taken, and the time is averaged to obtain the TBUT. A TBUT value of less than 10 seconds is considered abnormal. TBUT will be measured at Screening and at Day 84.

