9.3 Exploratory Efficacy Analyses

Meibomian gland dysfunction grading will be analyzed as an exploratory endpoint using the model above.

10 Safety Analyses

Adverse event (AE) data will be listed by subject within study center and IP. Tables of proportions of AEs by IP within body system, severity and relationship to IP will be provided.

Tables of All-Cause Mortality and Serious Adverse Events (SAE) will also be included.

No formal statistical analyses of AE data are planned.

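### The exploratory meibomian endpoint sets no condition on the Baseline grade, and no planned between-arm test clearly adjusts for it; the cost is lost sensitivity, not bias

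*Protocol*

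**What the plan says.** **Endpoint.** Protocol 11.6.3 defines it as "Proportion of subjects with meibomian gland dysfunction grade of 0 on both meibomian orifice size and telangiectasia scales in the study eye" at Day 84. SAP 4.2 repeats it: "The proportion of subjects with meibomian gland dysfunction grade of 0 on both meibomian orifice size and telangiectasia scales in the study eye". Neither mentions the Baseline grade.

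**Entry.** Protocol 9.2.1.2 states "A grade of 1 or 2 in meibomian orifice size in at least one eye is required for eligibility into the study". If only one eye qualifies, osmolarity and orifice grade "must be present in the same eye at both Screening and Baseline if only one eye qualifies". For the other scale: "A certain score on the telangiectasia scale is not required for study entry, nor is it an exclusion criterion". The same section says that the scales are meant to follow progress or resolution of the gland disease.

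**Study eye.** There are three rules.
- Synopsis, Protocol 6.1 and SAP 5.3: "The study eye will be the worse eye at Baseline as defined by higher tear osmolarity score". SAP 5.3 also requires at least 312 mOsm/L in the study eye at both visits, but no orifice grade in that eye.
- Protocol 11.1: the same ranking on osmolarity, but only among qualifying eyes.
- Protocol 11.6: lower TBUT first, then higher osmolarity, with no limit to qualifying eyes.

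**Test.** Protocol 11.6 allows chi-square, Fisher's exact or Cochran-Mantel-Haenszel (CMH) for binary data and names no grade stratum. SAP 9.3 says "Meibomian gland dysfunction grading will be analyzed as an exploratory endpoint using the model above". Model (1) in SAP 9 has center and treatment terms only. SAP 7.3 states adjustment for the pre-randomization value for the primary analysis.

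**The concern.** A rate of clear glands at Day 84 reads naturally as a resolution rate, but resolution requires something to resolve. Where a study eye can enter at 0 on both scales and stay there, it adds a success to either arm without any drug effect. Even where every study eye has orifice disease, telangiectasia at Baseline can run from 0 to 4. An eye that starts at 0 on that scale plausibly has less far to go than one that starts at 4.

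Both scales are scheduled at Screening, Baseline and Day 84, so a prognostic covariate is collected and then left out of the comparison. At stake are the power of this comparison and the meaning of the reported proportion. No primary or secondary conclusion depends on it.

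**Working it through.** **1. Is there a figure to reproduce?** No. The documents give no rate, effect size or power for this endpoint. The stated 95% powers for osmolarity, OSDI and TBUT do reproduce at 150 per arm (95.4%, 94.6%, 95.0%) but do not bear on it.

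**2. Can a study eye start at 0/0?** Take a right eye at 320 mOsm/L with orifice grade 1 and a left eye at 340 mOsm/L graded 0 on both scales, with similar values at Screening.
- The right eye qualifies the subject.
- Under the Synopsis, Protocol 6.1 and SAP 5.3, the left eye has the higher osmolarity and is the study eye. If it stays clear, it is a success.
- Under Protocol 11.1, only the right eye qualifies, so a 0/0 study eye is impossible.
- Under Protocol 11.6, TBUT decides, and the left eye may be chosen.

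**3. Dilution.** Assumptions: 150 per arm; a share f of study eyes at 0/0 at Baseline; 90% of these still 0/0 at Day 84 in both arms; resolution in the other eyes of 20% (OmegaD) and 10% (placebo).

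Observed rate = 0.9f + (1 − f)p, so the difference is (1 − f) × 10 points.

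Unadjusted power = Φ[(d − 1.96·SE0)/SE1], where d is the difference, SE0 the pooled and SE1 the unpooled standard error. For f = 0: d = 0.10, SE0 = √(2 × 0.15 × 0.85/150) = 0.0412, SE1 = √((0.09 + 0.16)/150) = 0.0408. This gives Φ(0.470) = 68%.

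| f | OmegaD vs placebo | Ratio | Unadjusted power | CMH by Baseline status (simulated) |
|---|---|---|---|---|
| 0% | 20.0% vs 10.0% | 2.00 | 68% | same test |
| 1% | 20.7% vs 10.8% | 1.92 | 65% | not tabulated |
| 2% | 21.4% vs 11.6% | 1.84 | 63% | 67–68% |
| 5% | 23.5% vs 14.0% | 1.68 | 56% | 65% |
| 10% | 27.0% vs 18.0% | 1.50 | 46% | 60–61% |
| 20% | 34.0% vs 26.0% | 1.31 | 33% | 52% |

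At f = 10%, eyes that were already clear supply 0.10 × 0.9 = 9 of the 18 points in the placebo rate.

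**4. No 0/0 eyes at all (the Protocol 11.1 case).** Assume 40% of study eyes start at telangiectasia 0.
- Rates of 30% vs 15% in those eyes and 4% vs 2% in the rest give overall rates of 0.4 × 30 + 0.6 × 4 = 14.4% and 0.4 × 15 + 0.6 × 2 = 7.2%. Stratifying raises power from about 53% to 56%.
- Rates of 50% vs 30% and 5% vs 2% give 23.0% and 13.2%. Stratifying raises power from about 60% to 71%.

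**5. Type I error.** With equal rates in both arms, the simulated rejection rate of the unadjusted and stratified tests stays near 5%. Simulated powers are good to about one point.

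**The case against.** **A 0/0 study eye may never occur.** Protocol 11.1 limits the study eye to qualifying eyes, which means orifice grade 1 or 2 at Baseline. This stands: under that rule the dilution in step 3 is zero. A reader might infer that clear eyes will certainly enter the count. The documents do not support that, because they contradict each other on which eye is analyzed.

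**If such eyes occur, they may be rare.** A 0/0 study eye must be the non-qualifying fellow eye, have the higher osmolarity (at least 312 mOsm/L at both visits under SAP 5.3), and be clear on both scales while the other eye is not. This also stands. Nothing in the documents supports a share of 10% or 20%. At 1% to 2%, power is 65% to 63% against 68%.

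**The Baseline grades are not idle.** A reader might infer that they go unused. They decide eligibility, and Protocol 11.6 summarizes categorical variables at each assessment. Only their use in the between-arm test is missing or unclear.

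**Randomization protects the comparison.** A reader might infer bias, or chance imbalance passing as a drug effect. Baseline grades balance on average, and the unadjusted test keeps its 5% level. What is lost is sensitivity.

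**The telangiectasia argument is ordinary covariate adjustment.** Agreed: no eye is miscounted there. It is still a gain from data already scheduled, and it holds under any of the three study-eye rules.

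**Conclusion.** The point holds as a minor one. The endpoint has no Baseline condition, and no planned between-arm test of it clearly uses the Baseline grades. Because telangiectasia is unrestricted at entry, Baseline grade is likely to matter whichever eye is chosen. Whether already-clear eyes can also count as successes depends on which of three conflicting study-eye rules applies.

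The consequence is reduced power and, where 0/0 study eyes are possible, a proportion that cannot be read purely as resolution. On the assumed rates, the power loss is a few points if 1% to 2% of study eyes start clear and 12 points at 5% (68% to 56%). It is larger only at shares for which the documents give no support. With no such eyes, stratifying gains roughly 3 to 11 points under the two assumed rate sets. All these figures rest on assumed rates. The endpoint is exploratory and carries no power claim, so no main trial conclusion changes.

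**What to change.** 1. Reconcile the study-eye rule across the Synopsis, Protocol 6.1, 11.1 and 11.6, and SAP 5.3, and say whether the study eye must itself meet the orifice criterion.
2. In SAP 9.3 and Protocol 11.6.3, name the binary Day 84 endpoint. Test it with CMH stratified by the study eye's Baseline grades, or with logistic regression that has both Baseline grades as covariates. Set the rule for collapsing sparse grades before unmasking, for example telangiectasia 0 against 1 or more.
3. Beside the all-subject proportion, report the resolution rate among study eyes not at 0/0 at Baseline. Do not restrict to orifice grade 1 or higher: that would also drop eyes at orifice 0 with telangiectasia, which do have something to resolve.

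The cost is a few lines of SAP text and code, with no new data. The downside is some collapsing of grades and a slightly smaller denominator in the restricted summary.
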